4.5 Timing of Efficacy Analyses and Safety Evaluations

Table 1. Summary of Analyses with Cutoff Dates and Data Included

	Analysis Number/Database Version	Cutoff Date	Efficacy/PRO Data Included	Safety Data Included
DMC	C	24 Apr 2017	Not included	All safety data ^a
DMC	I	03 Nov 2017	Not included	All safety data ^a
DMC	J	30 Apr 2018	Included	All safety data ^a

a. Safety population is defined in Section 5.1.2.

Efficacy and safety data up to and including the cutoff date specified in [Table 1](#) will be analyzed. During this data collection period, active subjects will continue to receive venetoclax, as applicable. When data collection is complete and all data management quality assurance (QA) and quality control (QC) procedures are performed, the clinical database data will be extracted for documentation and statistical analyses. Any active subjects will continue to receive venetoclax until they discontinue or for up to 2 years. Subjects that continue to derive clinical benefit after 2 years of treatment and where venetoclax is not commercially available may continue with treatment with venetoclax for up to 2 additional years. AbbVie will work with investigator on case by case basis to consider the potential continuation of the treatment. Once the last enrolled subject discontinues/completes the study, the study will be considered complete and all remaining data will be collected and entered into the clinical database.

All analyses will be conducted at AbbVie (or their designees) according to the methodologies specified in this SAP.

5.0 Analysis Populations

5.1 Definition for Analysis Populations

5.1.1 Efficacy Populations

5.1.1.1 Intent-to-Treat (ITT) Population

All enrolled subjects treated with at least one dose of venetoclax will be included in the ITT population. Efficacy analyses will be performed on the ITT population, unless otherwise specified.

5.1.1.2 ITT BCRI-Naive (ITT-BN) Population

ITT-BN population includes subjects who have not been previously treated with BCRI therapy in the ITT population.

5.1.1.3 ITT BCRI-Experienced (ITT-BE) Population

ITT-BE population includes subjects who were previously treated with BCRI therapy in the ITT population.

5.1.2 Safety Population

All ITT subjects will be included in the safety population.

5.2 Variables Used for Stratification of Randomization

No stratification is used for this open-label single-arm study.

6.0 Analysis Conventions

6.1 Baseline

Definition of Baseline

The baseline value (except for laboratory variables) is defined as the last non-missing measurement collected before the first dose of venetoclax. The baseline value for laboratory variables will be defined as:

- For subject with IV hydration for TLS prophylaxis, the baseline value will be the non-missing lab value taken before the subject receiving IV hydration prior to the first dose of venetoclax.
- For subject without IV hydration for TLS prophylaxis, the baseline value will be the non-missing lab value taken before the first dose of venetoclax.

6.2 Treatment Days

Definition of Treatment Days (Days Relative to the First Dose of Venetoclax)

Treatment (Rx) days are calculated for each time point relative to the first dose date of venetoclax. They are defined as the number of days between the day of the first dose of venetoclax and the specific time point. Rx days are negative values when the time point of interest is prior to the first venetoclax dose day. Rx days are positive values when the time point of interest is after the first venetoclax dose day. The day of the first dose of venetoclax is defined as Rx Day 1, while the day prior to the first venetoclax dose is defined as Rx Day -1 (there is no Rx Day 0).

Definition of Final Observation

The final observation (Final Visit) is defined as the last non-missing observation collected within 30 days following the last dose of venetoclax, unless otherwise specified.

6.3 Definition of Analysis Windows

For visit wise analyses including quality of life (QoL), the time windows specified in [Table 2](#) describe how the data are assigned to protocol specified visits. Analysis time windows are constructed using the following algorithm:

- Determine the nominal study Rx day for each scheduled visit.
- Determine the window around a specific nominal study Rx day as in [Table 2](#).
- If more than one assessment is included in a time window the most conservative value (i.e., the smallest score) should be used for the analysis of quality of life measures. A sensitivity analysis should be performed based on considering the most favorable (i.e., the largest value) assessment of the quality of life measures. Except the quality of life measures, if there are two observations with equal distance to the nominal day, the latest one will be used in analyses.

Table 2. Time Windows for Quality of Life

Scheduled Visit	Nominal Day	Time Window (Study Day Range)
Week 1 Day 1/Baseline	≤ 1	See the baseline definition (Section 6.0)
Week 4 Day 1	22	2 to 56
Week 12 Day 1	78	57 to 153
Week 24 Day 1	162	154 to 237
Week 36 Day 1	246	238 to 321
Week 48 Day 1	330	322 to 405
Week 60 Day 1	414	406 to 489
Week 72 Day 1	498	490 to 573
Week 84 Day 1	582	574 to 657
Week 96 Day 1	666	658 to 743
Week 108 Day 1	750	744 to 835
Final Observation	Last non-missing value within 30 days of last dose of Venetoclax	

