5.3.7.3 EuroQol 5 Dimensions (EQ-5D-5L)

The EuroQol 5 Dimensions (EQ-5D-5L) is a generic preference instrument that has been validated in numerous populations.^{41,42} The EQ-5D-5L has five dimensions: mobility, self-care, usual activities, pain/discomfort and anxiety/depression. These dimensions are measured on a five level scale: no problems, slight problems, moderate problems, severe problems, and extreme problems. The scores for the 5 dimensions are used to compute a single utility index score ranging from zero (0.0) to 1 (1.0) representing the general health status of the individual. The EQ-5D-5L also contains a visual analog scale (VAS) to assess the subject's overall health. The MID for the EQ-5D utility index score in cancer subjects is 0.08, and the MID for EQ-5D VAS is 7.^{43,44}

Each of the five dimensions of the EQ-5D-5L, the VAS and overall utility score will be calculated using the EuroQol scoring manual, and summarized (mean, std. dev., median) at each assessment. The impact of treatment over time will be assessed by calculating the change in score from baseline at each assessment time point.

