10.3 Additional Secondary Efficacy Analyses

Additional efficacy endpoints to be analyzed for the ITT, ITT-BN, and ITT-BE populations are Health Economic and Patient Reported Outcome measures, which include the FACT-Leu, FACIT-F, and the EQ-5D-5L (measure of general health status) and EQ-5D-VAS (Visual Analog Scale).

For the FACT-Leu, scores will be summarized descriptively at each assessment. The impact of treatment on quality of life over time will be assessed by calculating the change in scores from baseline at each assessment time point. Scores will be calculated according to the FACT-Leu scoring manual. The scores will also be summarized (mean, standard deviation, median) at each assessment. In addition mean change in scores (each assessment versus baseline) will be estimated. The 95% confidence interval of the mean change will be constructed based on (a) paired t-test and (b) with model assumption. A

linear mixed effect model will be used for the analysis of repeated measures where the covariance pattern will be assumed as compound symmetry (CS).

For the FACIT-F, scores will be summarized descriptively at each assessment. The impact of treatment on fatigue over time will be assessed by calculating the change in score from baseline at each assessment time point. Scores will be calculated according to the FACIT-F scoring manual. The scores will also be summarized (mean, standard deviation, median) at each assessment. In addition mean change in scores (each assessment versus baseline) will be estimated. The 95% confidence interval of the mean change will be constructed based on (a) paired t-test and (b) with model assumption. A linear mixed effect model will be used for the analysis of repeated measures where the covariance pattern will be assumed as compound symmetry (CS).

The EQ-5D-5L is a generic preference instrument that has been validated in numerous populations. The EQ-5D-5L has five dimensions: mobility, self care, usual activities, pain/discomfort and anxiety/depression. These dimensions are measured on a five level scale: no problems, slight problems, moderate problems, severe problems, and extreme problems. The EQ-5D-5L also contains a visual analog scale (VAS) to assess the subject's overall health.

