For each of the five dimensions of the EQ-5D-5L, the number and percentage of subjects at each level will be summarized at each assessment. The VAS values and the score of the EQ-5D-5L will also be summarized (mean, standard deviation, median) at each assessment; in addition mean change in VAS values and the score of the EQ-5D-5L (each assessment versus baseline) will be estimated. The 95% confidence interval of the mean change will be constructed based on (a) paired t-test and (b) with model assumption. A linear mixed effect model will be used for the analysis of repeated measures where the covariance pattern will be assumed as compound symmetry (CS).

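### If the EQ-5D-5L dimensions are coded in the order the plan lists them, the SAP's smallest-is-conservative rule puts the better answer in their main table and the worse one in the sensitivity table

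*SAP*

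**What the plan says.** SAP 6.3 sets the rule for windows holding more than one assessment. For the main analysis, "the most conservative value (i.e., the smallest score) should be used for the analysis of quality of life measures". It then adds: "A sensitivity analysis should be performed based on considering the most favorable (i.e., the largest value) assessment of the quality of life measures". No instrument or item is exempted.

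SAP 10.3 names the patient-reported measures, "which include the FACT-Leu, FACIT-F, and the EQ-5D-5L (measure of general health status) and EQ-5D-VAS". On the EQ-5D-5L dimensions it says: "These dimensions are measured on a five level scale: no problems, slight problems, moderate problems, severe problems, and extreme problems". They are analysed by visit: for each dimension, "the number and percentage of subjects at each level will be summarized at each assessment".

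Protocol 5.3.7.3 treats the dimension answers as numeric: "The scores for the 5 dimensions are used to compute a single utility index score". The same section plans a mean, standard deviation and median for each dimension, and refers to the EuroQol manual for scoring. Neither document prints the code given to each level.

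**The concern.** The SAP equates conservative with smallest and favorable with largest for every quality of life measure. That works only where a higher number means better health. The dimension levels are listed from best to worst, so coding in that order makes the smallest number the best answer.

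Two things would follow for a subject with two differing questionnaires in a window. The main dimension table would show the better answer although the SAP says it is conservative, and the sensitivity table would show the worse answer under the label favorable. Also, the main index and VAS would keep the lower (worse) value while the dimensions kept the better answer. A single visit could then show a poor index beside good dimension levels, although the index is computed from those dimensions.

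**Working it through.** The plan states no figure on this point, so there is none to reproduce. The check has four steps.

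**1. Direction of each measure**

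| Measure | Direction | Source | Smallest value is |
|---|---|---|---|
| FACT-Leu | higher is better | Protocol 5.3.7.1 | worse: rule fits |
| FACIT-F | lower is more fatigue | Protocol 5.3.7.2 | worse: rule fits |
| EQ-5D index | 0 to 1, general health status; higher as better is implied, not stated | Protocol 5.3.7.3 | worse, on that reading: rule fits |
| EQ-5D VAS | overall health; higher as better is implied, not stated | Protocol 5.3.7.3 | worse, on that reading: rule fits |
| EQ-5D-5L dimensions | "no problems, slight problems, moderate problems, severe problems, and extreme problems" | SAP 10.3 | depends on the coding |

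**2. The rule applied to the dimensions**

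Five levels give 5 × 4 = 20 ordered pairs of differing answers.

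- Codes 1 to 5 in the listed order: the smallest value is the better answer in 20 of 20 pairs. The main analysis keeps the worse answer in 0 of 20.
- Codes reversed: the smallest value is the worse answer in 20 of 20 pairs, and there is no fault.

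Example under the listed order: mobility is rated no problems (1) on one questionnaire and severe problems (4) on another in the same window. The main table keeps 1 and the sensitivity table keeps 4.

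**3. When the rule acts**

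SAP Table 2 places exactly one scheduled questionnaire in each window, so the rule needs an extra one. Protocol Appendix D supplies it: the questionnaires are also due at the Final Visit, which Protocol 5.3.1.1 wants as soon as possible after treatment stops. If that visit falls after the window's nominal day, it normally shares the window with a completed scheduled questionnaire.

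Days after the nominal day, out of all days in the window (Table 2):

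- Week 4 (nominal day 22, window 2 to 56): 34 of 55
- Week 12 (78, 57 to 153): 75 of 97
- Weeks 24, 36, 48, 60, 72 and 84: 75 of 84 each, so 450 of 504
- Week 96 (666, 658 to 743): 77 of 86

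Total: 34 + 75 + 450 + 77 = 636 of 55 + 97 + 504 + 86 = 742 days, or 86%. For a subject who stops early in Weeks 4 to 96, two questionnaires in one window is therefore the usual case. This percentage describes calendar days; it is not a percentage of subjects.

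**4. After rewording**

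With conservative defined as the worse health state, the main dimension table keeps the worse answer in 20 of 20 differing pairs and the sensitivity table keeps the better one, whichever coding is used.

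**The case against.** **The coding is not in the documents.** This stands. The levels are given only in words, and scoring is left to a manual that is not part of the plan. A reader might infer that the two tables are certainly swapped. The documents do not support that: the fault follows from coding in the listed order, which is the natural reading but is still an assumption.

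**The rule may not reach the dimensions.** SAP 6.3 speaks of scores and values. SAP 10.3 uses those words for the index and VAS, and tabulates the dimensions as categories. On that reading the rule is right for what it governs and silent on the dimensions. This is arguable but weaker. SAP 6.3 covers quality of life measures without exception, the EQ-5D-5L is one of them, and Protocol 5.3.7.3 gives the dimensions scores and means. A programmer might resolve the conflict from the stated intent, but a SAP meant to guide programming should not rely on that.

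**Little is lost.** This also stands. Both selections are produced, so the error is one of labelling. The Final Observation row in Table 2 also still shows the last questionnaire.

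**Mixed questionnaires are a separate matter.** This is correct. Selecting value by value can draw on different questionnaires even when every direction is right. The reversed direction makes a conflict between dimensions and index more likely, but correcting it does not remove all mixing.

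**A numerical size.** A reader might assume that 10% to 20% of subjects have two questionnaires at each visit and derive a shift of a few points in the share with no problems. The schedule does not support that rate. Duplicates come mainly from one Final Visit per subject, apart from visits moved after dose interruptions. Over the nine windows before Week 108, such a rate would mean that 1 − 0.9^9 = 61% to 1 − 0.8^9 = 87% of subjects stopped early. Nothing in the documents suggests this. The level distribution and within-subject correlation that such a figure would need are also absent.

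**Conclusion.** The point holds conditionally. If the dimension levels are coded in the listed order, SAP 6.3 gives the opposite of its stated intent for the EQ-5D-5L dimensions, in every window where the answers differ. If they are reverse-coded, there is no fault.

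The reach is narrow. FACT-Leu and FACIT-F are handled correctly, and so are the EQ-5D index and VAS if higher is better. Windows with one questionnaire, or with identical dimension answers, are unaffected. The tables are descriptive secondary outcomes; the primary CR + CRi analysis and the sample size are untouched. No percentage-point effect can be given from the documents. This is a minor point, worth correcting because the correction is cheap.

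**What to change.** In SAP 6.3, define conservative as the worse health state and favorable as the better health state for each measure. For FACT-Leu, FACIT-F, the EQ-5D index and the VAS, that means the smallest and largest values respectively. For each EQ-5D-5L dimension, the highest problem level is conservative and the lowest is favorable. State the dimension coding in the SAP.

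If the dimensions and index should also agree within a visit, use this alternative for the dimensions: take all five from the questionnaire that supplies the selected index value, lowest for the main analysis and highest for the sensitivity analysis. A single dimension may then not be the worse of its two answers, but the profile will be one the subject actually gave. This version needs a line for tied index values and for questionnaires without an index, because SAP 6.4 does not impute missing EQ-5D-5L items.

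The cost is a sentence or two in the SAP and a programming flag. No data collection changes.

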6.4 Missing Data Imputation

If a respondent answers at least 50% of the items in FACIT-F, the missing items will be imputed with the average score of the answered items in the same scale. In cases where the respondent did not answer at least 50% of the items, the score for that domain will be considered missing. Similarly, the missing items of the FACIT-Leu questionnaire will be imputed with the average score of the answered items in the same scale as long as more than 50% of the items in the scale are answered. For EQ-5D-5L index, no imputation will be performed for missing items.

Subjects with missing disease progression date, missing death date, or missing last known alive date will be considered as censored subjects for time to progression, progression free survival analysis, and survival analysis. And the subject will be censored at the interim data cutoff date.

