5.4 Removal of Subjects from Therapy or Assessment

5.4.1 Discontinuation of Individual Subjects

Each subject has the right to withdraw from the study and/or study drug treatment at any time. In addition, the investigator may discontinue a subject from study drug treatment at any time if the investigator considers it necessary for any reason including:

- The investigator believes it is in the best interest of the subject
- Subject's response to therapy is unsatisfactory, as evidenced by progression of disease while on study drug
- The subject requires other cancer treatment (e.g., radiotherapy, cancer-related surgery as a result of tumor progression, alternate anti-neoplastic agents) during the study period
- unacceptable toxicity
- The subject becomes pregnant while on the study

- drug/protocol non-compliance

The investigator will inform AbbVie prior to discontinuing a subject from the study by contacting the Clinical Team Leader as identified in Section 7.0. All subjects will be included for analysis of safety data. Subjects who withdraw from the study will not be replaced unless they are not evaluable.

Subjects will continue to be followed for unresolved AEs and survival information for any subject who has not experienced PD at the time of venetoclax discontinuation.

Final Visit

Upon study drug discontinuation and/or upon discontinuation from the study, the reason(s) for discontinuation will be recorded in electronic case report forms (eCRFs) and a final visit will be performed. The final visit procedures as listed in [Appendix D](#) should be performed as soon as possible after discontinuation from study drug.

30-Day Safety Follow-Up Visit

A 30-Day Safety Follow-up Visit should be performed approximately 30 days (\pm 3 days) following the last dose of venetoclax. The 30 day safety follow up procedures listed in [Appendix D](#) should be performed.

Post Treatment and Survival Follow-Up Calls

For subjects who discontinue venetoclax therapy, but do not discontinue the study, post treatment follow-up calls will be performed every 6 months (\pm 7 days) for survival information (i.e., disease progression, the date and cause of death, post-treatment cancer therapies, etc.) and will be collected via telephone calls for a period of 2 years and recorded in the eCRFs.

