8.1.2.2 Secondary Efficacy Endpoints

Key secondary efficacy endpoints will include overall response rate, duration of response, time to progression, progression-free survival, overall survival, and the CR rate in previously BCRi treated subjects.

ORR will be assessed as the proportion of subjects with an overall response (CR + CRi + nPR + PR) based on the IWCLL NCI-WG criteria. The ninety-five percent (95%) confidence interval based on binomial distribution will be constructed for the calculated CR rate.

Duration of response will be defined as the number of days from the date of first response (CR, CRi, nPR, or PR) to the earliest recurrence or PD. If a subject is still responding, then the subject's data will be censored at the date of the subject's last available disease assessment. For subjects who never experience response, the subject's data will be censored on the date of enrollment. Duration of response will be analyzed by Kaplan-Meier methodology using data for all enrolled subjects. Median duration of response will be calculated and the corresponding 95% confidence interval will be presented.

Time to progression (TTP) will be defined as the number of days from the date of first dose or enrollment if not dosed to the date of earliest disease progression. All disease progression will be included regardless whether the event occurred while the subject was taking the study drug or had previously discontinued the study drug. If the subject does not experience disease progression, then the data will be censored at the date of last available disease assessment. Data for subjects who receive non-protocol, CLL therapy prior to disease progression will be censored at the last disease assessment prior to receiving non-protocol therapy. Data for subjects without any disease assessments performed after the baseline visit will be censored at the time of enrollment plus 1 day. TTP will be analyzed by Kaplan-Meier methodology using data for all subjects enrolled. Median time TTP will be calculated and 95% confidence interval for median time TTP will be presented.

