10.1.1 Definitions for Efficacy Endpoints

Complete Remission Rate (CR + CRi)

Complete response rate, complete remission (CR) or complete remission with incomplete marrow recovery (CRi), will be defined as the proportion of subjects per the 2008 Modified IWCLL NCI-WG criteria as assessed by investigator using the best response at any time during the study. In addition, the 95% confidence interval for complete response rate (CR) rate based on the binomial distribution (Clopper-Pearson exact method) will be provided. Subjects who do not achieve a CR or CRi will be considered to be non-responders in the calculation of complete response rate.

Overall Response Rate (ORR)

ORR (CR + CRi + nPR + PR) will be defined as the proportion of subjects who achieved complete remission (CR), complete remission with incomplete marrow recovery (CRi), nodular partial remission (nPR), or confirmed partial remission (PR) based on the 2008 Modified IWCLL NCI-WG criteria as assessed by investigator using the best response at any time during the study. Confirmatory PR response will be determined by not less than 49 days from the first PR was observed. The corresponding exact 95% confidence interval for the proportion (Clopper-Pearson exact method) will be constructed. Subjects who do not respond will be considered non-responders.

Duration of Response (DOR)

The DOR for a given subject will be defined as the number of days from the day the criteria are met for CR, CRi, nPR, or confirmed PR (whichever is recorded first) to the earliest date that progressive disease (PD) is objectively documented (radiographic or clinical) or death (i.e., $DOR = PD/death/censoring\ date - earliest\ CR/CRi/nPR/PR\ date + 1\ day$). For subjects who have a PR before CR, CRi, or nPR in subsequent visits, the DOR is computed from the earliest PR. If a subject is still responding then the subject's data will be censored at the date of the last available disease assessment prior to the data cutoff date. Only subjects with the iWCLL response criteria will be included in the analysis of DOR. The distribution of the duration of overall response will be estimated using the Kaplan-Meier methodology. Median duration of response will be calculated and the corresponding 95% confidence interval will be presented.

Time to Progression (TTP)

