Overall survival (time to death) for a given subject will be defined as the number of days from the first dose date of venetoclax to the date of the subject's death (i.e., $OS = death/censoring\ date - first\ dose\ date + 1\ day$). All events of death will be included, regardless of whether the event occurred while the subject was still taking any study drug, or after the subject discontinued any study drug. If a subject has not died, then the data will be censored at the date when the subject was last known to be alive prior to the cutoff date. The date of the last known to be alive will be determined by selecting the last available date of the following study procedures for a subject: study visit/contact date, tumor assessment, clinical disease progression, physical examination, vital signs assessment, clinical laboratory collection, study drug, adverse event assessment, concomitant medication assessment, drug or study completion, survival visit, and post treatment therapy assessment. The distribution of the time to death will be estimated

using Kaplan-Meier methodology. Median survival time and the corresponding 95% confidence interval will be estimated.

Minimal Residual Disease (MRD) Response Rate

The rate of MRD response in CLL subjects will be defined as the proportion of CLL subjects who achieved MRD negative status with less than one CLL cell per 10,000 leukocytes (or below 10^{-4}). All subjects with an MRD assessment will be included in the denominator for the calculation of MRD response rate. Minimal residual disease response will be summarized by categories: MRD negative, MRD positive, or MRD unknown/missing. The 95% confidence intervals based on the binomial distribution (Clopper-Pearson exact method) will be provided.

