11.2 Analysis of Treatment-Emergent Adverse Events

All summaries/analyses involving AEs will include treatment-emergent adverse events (TEAE) only, unless otherwise specified. TEAE are defined as any event with onset after the first dose of venetoclax and no more than 30 days after the last dose of venetoclax. Events where the onset date is the same as the venetoclax start date are assumed to be treatment-emergent, unless the venetoclax start time and the AE start time are collected and the AE start time is prior to the venetoclax start time. If an incomplete onset date was collected for an AE, the AE will be assumed to be treatment-emergent unless there is evidence that confirms that the AE was not treatment-emergent (e.g., the AE end date was prior to the date of the first dose of venetoclax).

Treatment-emergent adverse events will be summarized by maximum severity grade level of each preferred term. Each adverse event will be assigned a grade level (grade 1, 2, 3, 4, or 5) by the investigator. If a subject has an AE with unknown severity, then the subject will be counted in the severity grade level category of "unknown," even if the subject has another occurrence of the same event with a severity present. The only exception is if the subject has another occurrence of the same AE with the highest grade level (grade 5). In this case, the subject will be counted under the "Grade 5" category.

Treatment-emergent adverse events will be summarized by relationship of each preferred term to venetoclax, as assessed by the investigator. If a subject has an adverse event with

unknown relationship, then the subject will be counted in the relationship category of "unknown," even if the subject has another occurrence of the same event with a relationship present. The only exception is if the subject has another occurrence of the same adverse event with a relationship assessment of "Reasonable Possibility." In this case, the subject will be counted under the "Reasonable Possibility" category.

Adverse events will be coded using the Medical Dictionary for Regulatory Activities (MedDRA). The actual version of the MedDRA coding dictionary will be noted in the clinical study report.

Adverse event data will be summarized and presented using primary MedDRA system organ classes (SOCs) and preferred terms (PTs) according to the MedDRA coding dictionary version 20.1 or higher.

Adverse Event

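### SAP 6.4 censors a known but undated progression or death at an undefined cutoff, which can only push TTP, PFS and OS upward

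*SAP*

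**What the plan says.** SAP Section 6.4 (Missing Data Imputation) states: "Subjects with missing disease progression date, missing death date, or missing last known alive date will be considered as censored subjects". It applies this to TTP, PFS and OS; DOR is not named. It then adds: "And the subject will be censored at the interim data cutoff date".

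Other parts of the plan bear on the same subjects:

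- **SAP 10.1.1, TTP and PFS:** a subject without an event is censored at the last available disease assessment before the data cutoff.
- **SAP 10.1.1, OS:** "All events of death will be included, regardless of whether the event occurred while the subject was still taking any study drug", or after it was stopped. A survivor is censored at the date last known alive.
- **SAP 10.1.1, DOR:** the endpoint runs to the "earliest date that progressive disease (PD) is objectively documented (radiographic or clinical) or death".
- **Protocol 8.1.2.2, TTP and PFS:** "All disease progression will be included regardless whether the event occurred" on or off study drug.
- **SAP 11.2, adverse events:** "If an incomplete onset date was collected for an AE, the AE will be assumed to be treatment-emergent", unless evidence shows otherwise.
- **SAP 4.5:** "Efficacy and safety data up to and including the cutoff date specified in" Table 1 are to be analysed. Table 1 lists three cutoffs, all labelled DMC. Only 30 Apr 2018 includes efficacy data, and none is called interim. Protocol 8.1.3 left the exact efficacy cutoff to the SAP.

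**The concern.** Under the heading of missing data, the natural case is an event that the record shows to have happened but for which the date is absent. Section 6.4 removes that event and credits the subject with event-free time to the cutoff. For OS, a subject known to be dead is counted as alive until then. The censoring is triggered by the event itself, so it is informative, and it always works in favour of the drug.

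Undated events are plausible here. Off treatment, progression and death are collected by telephone: "post treatment follow-up calls will be performed every 6 months". A call can establish that an event took place without establishing when.

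At stake are the Kaplan-Meier curves and medians for TTP, PFS and OS, overall and in the BCRi-naive and BCRi-experienced populations. These are estimates from a single arm, so a one-directional bias goes straight into the reported figure.

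There are three smaller gaps. DOR has no stated rule for an undated event in a responder. The cutoff term is undefined. The third trigger, a missing last-known-alive date, is nearly empty: SAP 5.1.1.1 admits only dosed subjects, and SAP 10.1.1 lets study drug supply such a date.

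**Working it through.** The plan states no event count, median or missing-date rate for these endpoints, so there is no figure of its own to reproduce.

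**Direction.** In the Kaplan-Meier estimator, an undated event under 6.4 contributes no drop and leaves the subject in the risk set to the cutoff. The curve is therefore higher from the true event date onward and never lower. This needs no distributional assumption.

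**Size: inputs.** N = 250 is from SAP 4.2. The rest are assumptions: exponential event times with medians m of 18, 30 and 60 months; follow-up spread uniformly over 12 to 24 months (30 Apr 2018 is 26 months after the original protocol date of 24 February 2016); and a random share p of events undated.

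**Formula.** Let F(t) be the true cumulative event probability and f(t) its density. Among subjects followed at least to t, the proportion at risk under 6.4 is 1 − F(t) + pF(t), and dated events occur at rate (1 − p)f(t). The hazard that Kaplan-Meier estimates is (1 − p)f(t) / [1 − (1 − p)F(t)]. In large samples the curve is then 1 − (1 − p)F(t), against a true 1 − F(t).

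Overstatement at time t = p × F(t), with F(t) = 1 − 2^(−t/m).

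**12-month rate, overstatement in percentage points:**

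| m (months) | F(12) | p = 2% | p = 5% | p = 10% |
|---|---|---|---|---|
| 18 | 0.370 | 0.74 | 1.85 | 3.70 |
| 30 | 0.242 | 0.48 | 1.21 | 2.42 |
| 60 | 0.129 | 0.26 | 0.65 | 1.29 |

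A simulation of 2000 trials per cell agrees: 0.71/1.90/3.71, 0.48/1.21/2.43 and 0.25/0.65/1.29. The mean number of undated subjects was 2.4/6.3/12.4, 1.7/4.2/8.5 and 0.9/2.3/4.7.

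**18-month rate.** A separate simulation with medians of 12, 30 and 60 months gave +0.9 to +3.2 points at 5% undated and +1.9 to +6.5 at 10%. The formula agrees: for m = 12, F(18) = 1 − 2^(−1.5) = 0.646, and 0.05 × 0.646 = 3.2 points.

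**Median.** The reported median solves (1 − p)F(t) = 0.5, so t = m × log2{1 / [1 − 0.5/(1 − p)]}. For a true median of 18 months:

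- p = 2%: 18 × 1.030 = 18.5 months
- p = 5%: 18 × 1.078 = 19.4 months
- p = 10%: 18 × 1.170 = 21.1 months

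In simulated trials of 250 that reached the median, the values were 18.5, 19.3 and 20.3. At 10% undated, 22% of trials did not reach it, against 2% with all dates known.

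**An alternative rule.** Take contacts every 6 months with random phase, 10% undated and a true median of 18 months. Keeping the event and imputing a date between the last event-free record and the first record of the event gives a 12-month error of −0.03 points at the midpoint, −0.58 at the earliest bound and +0.80 at the latest. The present rule gives +3.71.

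**The case against.** The strongest opposing points are these.

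- **Reading.** Section 6.4 does not say that the event was recorded. It could mean only that no date implies no event. On that reading no known event is lost. But subjects without an event would then be censored at the cutoff, which contradicts the last-assessment and last-known-alive dates in 10.1.1. Either reading requires a rewrite.
- **The inclusion clauses.** The statements that all deaths and all progressions count are mainly about events on versus off treatment and do not address undated events. That is fair. Still, nothing in them excludes undated events, and the conflict over censoring dates does not depend on them.
- **The adverse-event comparison.** Counting an AE needs no exact date, while Kaplan-Meier does. SAP 11.2 also speaks of incomplete dates and 6.4 of missing ones. The parallel shows a difference of approach rather than a contradiction.
- **Frequency.** The protocol lists the dates of death and progression among the items to collect, and nothing shows that undated events are common. This stands, and it is why the size is given as a range.
- **Precision.** With N = 250, the binomial standard error of the 12-month rate is about 3.1, 2.7 and 2.1 points for medians of 18, 30 and 60 months. The bias is below one standard error in every cell at 2% and 5%. This also stands, but the confidence interval is centred on the shifted estimate and does not account for the bias.
- **DOR and the cutoff.** Documented progression has a date source for DOR, so the gap there is mostly undated death. A reader can infer 30 Apr 2018 as the cutoff. Both are secondary points.

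**Conclusion.** The concern holds. As written, 6.4 discards known events and adds event-free time up to an undefined date. The direction is certain whenever the rule meets a known event.

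The size depends on the share of undated events, which the documents do not give. Under the stated assumptions the effect is negligible below about 2%, reaches 0.65–1.85 points on the 12-month rate at 5%, and 1.3–3.7 points at 10%. It should be corrected, but it is not critical: it touches descriptive secondary estimates only. The primary CR + CRi rate is unaffected, and SAP 10.1 plans no efficacy testing.

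**What to change.** Replace the second paragraph of SAP 6.4 with the following rules:

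1. A recorded progression or death with a partial or missing date remains an event for TTP, PFS, DOR and OS, as applicable to each endpoint.
2. Its date is imputed by one pre-specified rule between the last date documented event-free (last assessment without progression, or last known alive) and the first record of the event, respecting any known month or year. The midpoint is one suitable choice.
3. The earliest and latest bounds are run as sensitivity analyses.
4. The number of imputed dates is reported per endpoint.
5. Subjects without a recorded event are censored only as in Section 10.1.1.

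Replace the interim data cutoff term with the defined analysis cutoff, or delete it.

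The cost is one paragraph and a few lines of programming, with no new data. TTP, PFS and OS become slightly less favourable, and imputation adds a little uncertainty: at most −0.6 to +0.8 points on the 12-month rate in the 10% scenario above.
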